9.4.7 SUB-GROUP ANALYSES

Subgroup analysis of the primary efficacy endpoint such as demographic or other baseline patient characteristics will be performed. **Potential Sub-groups**

1. Sex
2. Age groups (< 70 vs. ≥ 70 years)
3. Race
4. Ethnicity
5. mRS 3 vs. 4
6. FMA-UE score
7. 10MWT score
8. Received tPA/thrombectomy for the index stroke
9. SAFE score at baseline (<5, 5-7, 8 or more)
10. First stroke or not
11. Right/left sided stroke
12. Stroke mechanism
13. Time from event to first treatment (< 14 days vs. ≥ 15 days)

14. Compliant vs. not-compliant⁵⁰
15. Treatment group assignment guess by the subject (blinding assessment)

Pooling

Subgroup analysis of the primary efficacy endpoint by site will be used to evaluate the poolability of the results. The significance of site-to-site variability in treatment effect will be evaluated by including site to the visit by group interaction term and will be added to the primary model. If the interaction time by site by group is found significant at a 15% level of significance, the reason for this will be further explored and rationalized. This evaluation may include demographic and baseline features, clinical and treatment history, and site comparability in the features found to be associated with the primary efficacy variable.

9.4.8 TABULATION OF INDIVIDUAL PARTICIPANT DATA

Listings of the efficacy and safety measurements will be provided.

9.4.9 EXPLORATORY ANALYSES

MoCA, ALDS and PHQ-8 scores at 90 days post stroke will be compared between the groups with analysis of variance adjusting for baseline value, if relevant (§ 9.4.2). The change from baseline to day 180 in mRS, SIS Hand Domain and EQ-5D-5L score at day 180, will be compared between the groups with analysis of variance adjusting for baseline value, if relevant. Safety through 180 days will also be summarized. Additionally, Bang's blinding index will be assessed (120).

Health economics data will be collected and analyzed for publication and other scientific purposes, but this is not intended to support regulatory submissions.

Relationship between adherence to treatment as measured by the Qompass and the clinical outcomes will be explored.

9.4.10 ADHERENCE AND RETENTION ANALYSES

The numbers of subjects who were enrolled and completed each visit of the study will be provided, as well as the reasons for all enrollment discontinuations, grouped by major reason (eg,

⁵⁰ The compliance analysis will be conducted as an exploratory sensitivity analysis assessing the correlation of number of completed treatments with the primary efficacy endpoint.

	The efficacy of a frequency-tuned electromagnetic field treatment in facilitating the recovery of subacute ischemic stroke patients – a pivotal study		
	No. BQ5	Ver. 4	Page 86 of 150

lost to follow-up, adverse event, poor compliance). A list of discontinued patients, protocol deviations, and patients excluded from the efficacy analysis will be provided as well. The effects of non-compliance, dropouts, and possible covariates such as age and sex will be assessed to determine the impact on the general applicability of results from this study.

10 SUPPORTING DOCUMENTATION AND OPERATIONAL CONSIDERATIONS

10.1 REGULATORY, ETHICAL, AND STUDY OVERSIGHT CONSIDERATIONS

10.1.1 INFORMED CONSENT PROCESS

10.1.1.1 CONSENT/ASSENT AND OTHER INFORMATIONAL DOCUMENTS PROVIDED TO PARTICIPANTS

Consent forms describing in detail the study device, study procedures and risks are given to the participant and written documentation of informed consent is required prior to starting administration of the study device.

IMPORTANT NOTE: If an Investigator uses the BQ 2.0 without obtaining informed consent, the Investigator shall report such use to the Sponsor and the reviewing IRB within 5 working days after the use occurs⁵¹.

10.1.1.2 CONSENT PROCEDURES AND DOCUMENTATION

The informed consent process will comply with 21 CFR Part 50 and the recommendations set out in INTEGRATED ADDENDUM TO ICH E6(R1): GUIDELINE FOR GOOD CLINICAL PRACTICE E6(R2) (§ 4.8 -- Informed Consent of Trial Subjects). A copy of the full guidelines may be found on the ICH website⁵². The U.S. FDA *draft guidance Informed Consent Information Sheet Guidance for IRBs, Clinical Investigators, and Sponsors* (July 2014) will be followed.

In obtaining and documenting informed consent, the Investigator will comply with the applicable regulatory requirement(s) and will adhere to GCP and to the ethical principles that have their origin in the Declaration of Helsinki, adopted by the 18th World Medical Assembly in Helsinki, Finland, in 1964, as last amended by the World Medical Assembly.

Prior to the beginning of the trial, the Investigator must have the IRB (and, where applicable regulatory authority) written approval/favorable opinion of the written informed consent form

⁵¹ 21 CFR 812.150(a)(5)

⁵² https://database.ich.org/sites/default/files/E6_R2_Addendum.pdf

	The efficacy of a frequency-tuned electromagnetic field treatment in facilitating the recovery of subacute ischemic stroke patients – a pivotal study		
	No. BQ5	Ver. 4	Page 87 of 150

(ICF) and any other written information to be provided to subjects. The Sponsor will supply a proposed ICF, which complies with regulatory requirements and is considered appropriate for the study. Any changes to the proposed consent form suggested by the Investigator must be agreed to by the Sponsor before submission to the IRB and local regulatory authority (if applicable) and a copy of the approved version must be provided to the Sponsor after IRB approval

Neither the Investigator, nor the trial staff, should coerce or unduly influence a subject to participate or to continue to participate in a trial.

The Investigator, or a person designated by the Investigator, must fully inform the subject or, if the subject is unable to provide informed consent, the subject's legally acceptable representative, of all pertinent aspects of the trial including the written information given approval/favorable opinion by the IRB.

Before informed consent may be obtained, the Investigator, or a person designated by the Investigator, must provide the subject or the subject's legally acceptable representative ample time and opportunity to inquire about details of the trial and to decide whether or not to participate in the trial. All questions about the trial must be answered to the satisfaction of the subject or the subject's legally acceptable representative. The Investigator or his/her designee should also stress that the subject is completely free to refuse to take part or withdraw from the trial at any time. Prior to a subject's participation in the trial, the written ICF must be signed and personally dated by the subject or by the subject's legally acceptable representative, and by the person who conducted the informed consent discussion.

If a subject is unable to read or if a legally acceptable representative is unable to read, an impartial witness must be present during the entire informed consent discussion. After the written ICF and any other written information to be provided to subjects is read and explained to the subject or the subject's legally acceptable representative, and after the subject or the subject's legally acceptable representative has orally consented to the subject's participation in the trial, and, if capable of doing so, has signed and personally dated the ICF, the witness must sign and personally date the consent form. By signing the consent form, the witness attests that the information in the consent form and any other written information was accurately explained to, and apparently understood by, the subject or the subject's legally acceptable representative, and that informed consent was freely given by the subject or the subject's legally acceptable representative.

Prior to participation in the trial, the subject or the subject's legally acceptable representative must receive a copy of the signed and dated written ICF and any other written information provided to the subjects.

	The efficacy of a frequency-tuned electromagnetic field treatment in facilitating the recovery of subacute ischemic stroke patients – a pivotal study		
	No. BQ5	Ver. 4	Page 88 of 150

During a subject's participation in the trial, the subject or the subject's legally acceptable representative must receive a copy of the signed and dated consent form updates and a copy of any amendments to the written information provided to subjects.

With the subject's prior consent, the subject's general practitioner may also be informed that they are taking part in the trial. An electronic general practitioner letter template may be provided for this purpose.

The written ICF and any other written information to be provided to subjects will be revised whenever important new information becomes available that may be relevant to the subject's consent. Any revised written ICF, and written information must receive the IRB/EC (and, where applicable regulatory authority) approval/favorable opinion in advance of use. The subject or the subject's legally acceptable representative must be informed in a timely manner if new information becomes available that may be relevant to the subject's willingness to continue participation in the trial. The communication of this information should be documented. If relevant, all affected subjects shall be asked to confirm their continuing informed consent in writing.

10.1.2 STUDY DISCONTINUATION AND CLOSURE

This study may be temporarily suspended or prematurely terminated if there is sufficient reasonable cause. Written notification, documenting the reason for study suspension or termination, will be provided by the suspending or terminating party to study participants, Investigator(s), Sponsor and regulatory authorities, where applicable. If the study is prematurely terminated or suspended, the Investigator will promptly inform study participants, IRB/EC, and Sponsor, and will provide the reason(s) for the termination or suspension. Study participants will be contacted, as applicable, and be informed of changes to study Visits schedule.

Circumstances that may warrant termination or suspension include, but are not limited to:

- Determination of unexpected, significant, or unacceptable risk to participants;
- Determination of possible serious health threat;
- Demonstration of efficacy that would warrant stopping;
- Insufficient compliance to protocol requirements and/or good clinical practice and/or regulatory requirements;
- Data that are not sufficiently complete and/or evaluable;
- Insufficient study enrollment;
- Investigational product supply or manufacturing issues;
- The Sponsor's decision to modify or discontinue product development;
- A request to discontinue the study by a regulatory or health authority.

	The efficacy of a frequency-tuned electromagnetic field treatment in facilitating the recovery of subacute ischemic stroke patients – a pivotal study		
	No. BQ5	Ver. 4	Page 89 of 150

Study-wide administration of study device will be halted if Grade ≥ 4 AEs determined to have “probable” or “causal” relationship are reported to the Sponsor. The Sponsor will notify the Investigators immediately when the event is reported, and enrollment screens will stop accepting new study participants. Where required, the Sponsor will inform the regulatory authorities of the temporary halt and the disposition of the study.

Similarly, if suspicion of an unacceptable risk, including serious health threat, to subjects arises during the trial, or when so instructed by the IRB/EC or regulatory authorities, the Sponsor shall suspend the clinical investigation while the risk is assessed. The Sponsor shall terminate the clinical investigation if an unacceptable risk which cannot be mitigated is confirmed⁵³.

DSMB will be established in the study (refer to § 10.1.6 for details), and the Sponsor will inform the DSMB members within 24 hours of this occurrence and will provide the DSMB with AE listing reports. The DSMB will convene an ad hoc meeting by teleconference or in writing as soon as possible and will provide recommendations for proceeding with the study to the study Sponsor.

Study may resume once concerns about safety, protocol compliance, and data quality are addressed, and satisfy the sponsor, IRB/EC and/or regulatory authority(ies).

When a study is prematurely terminated, refer to § 7 for handling of enrolled study participants

10.1.3 CONFIDENTIALITY AND PRIVACY

Subject confidentiality is strictly held in trust by the participating Investigators, their staff, and the Sponsor and its agents. This confidentiality is extended to cover testing of biological samples in addition to the clinical information relating to participants. Therefore, the study protocol, documentation, data, and all other information generated will be held in strict confidence and stored in accordance with the applicable local laws and/or regulations.

In compliance with guidelines regarding the monitoring of clinical studies and in fulfillment of the Investigator’s obligation to the Sponsor, it is required that he/she permit the Sponsor’s study Monitor and/or applicable regulatory authority representative to review that portion of the subject’s medical record that is directly related to the study. This shall include all study relevant documentation (including medical history to verify eligibility, laboratory tests results to verify transcription accuracy, treatment and diagnostic reports, admission/discharge summaries for hospital admissions occurring while the subject is on study and autopsy reports for deaths occurring during or in temporal proximity to the study).

⁵³ § 7.4.4 and 8.2.1 of ISO 14155:2020

	The efficacy of a frequency-tuned electromagnetic field treatment in facilitating the recovery of subacute ischemic stroke patients – a pivotal study		
	No. BQ5	Ver. 4	Page 90 of 150

As part of the required content of informed consent, the subjects must be informed that their records will be reviewed by the study Monitors or representatives of regulatory authorities. The subjects will also be informed that representatives of the DSMB may inspect their medical records to verify the information collected, and that all personal information made available for inspection will be handled in strictest confidence and in accordance with local data protection laws.

Should access to the medical record require a separate waiver or authorization, it is the Investigator's responsibility to obtain such permission from the subject in writing before the subject is entered into the study.

All information provided to the Investigator by the Sponsor, including nonclinical data, protocols, CRFs, and verbal and written information, will be kept strictly confidential and confined to the clinical personnel involved in conducting this study, and no disclosure shall be made except in accordance with any right of publication granted to the Investigator.

The study Monitor may inspect all documents and records required to be maintained by the Investigator, including but not limited to, medical records (office, clinic or hospital) and pharmacy records for the subjects in this study. The clinical study site will permit access to such records.

Throughout this study, the subject data will only be linked to the Sponsor's clinical study database or documentation framework via a unique identification number. As permitted by all applicable laws and regulations, limited subject attributes, such as sex, date of birth (to the extent permitted) and/or age, and subject initials (where permitted) may be used to verify the subject and accuracy of the subject's unique identification number. If the subject's name appears on any documents (eg, laboratory analysis report) it must be obliterated before a copy of the document is supplied to the Sponsor for data management or other purposes. Medical information may be provided to the participant's general practitioner or other appropriate medical personnel responsible for the subject's welfare. The subject's contact information will be securely stored at each clinical site for internal use during the study.

Trial findings stored on computer will be stored in accordance with local data protection laws. The Sponsor and any of its designees will maintain the confidentiality of all subject data and will not disclose information by which subjects may be identified to any third party, other than those directly involved in the treatment of the subject's condition. If the results are published, the subject's identity will remain confidential.

At the end of the study, all records will continue to be kept in a secure location for as long a period as detailed in § 10.1.9.2. Subject's research data, collected for purposes of statistical analysis and scientific reporting, will be transmitted to and stored by the Sponsor. This will not

include the subject's contact or identifying information. Rather, individual subjects and their research data will be identified by a unique identification number. The study data entry and study management systems used by clinical sites and by the Sponsor's research staff will be secured and password protected.

10.1.4 FUTURE USE OF STORED SPECIMENS AND DATA

Data collected for this study will be analyzed and stored either in the computers of the EDC system provider (refer to § 10.1.9.1 for details). In the event that a paper CRF replaces, temporarily or permanently, the electronic version, data collected using paper forms will be stored at the Sponsor's premises. After the study is completed, the de-identified, archived data will be transmitted to and stored at the Sponsor's premises, under the supervision of the Sponsor, for use by other researchers including those outside of the study. Permission to transmit the data to and store it at the Sponsor's premises will be included in the informed consent. When the study is completed, access to study data will be provided through and by the Sponsor.

Collection of biological samples is not planned in this protocol.

10.1.5 KEY ROLES AND STUDY GOVERNANCE

A list of the study Investigators and participating sites will be provided for inclusion in the trial master file and updates to the list will be provided during the trial.

Study Steering Committee (SSC) will be established and the study and will operate in accordance with a trial-specific charter. List of members of the SSC will be provided for inclusion in the trial master file and updates to the list will be provided during the trial. Its non-independent members may include the study Coordinating Investigator and may also include clinical collaborators and other identified collaborators, and the trial co-coordinators. The Sponsor and the study statistician will be allowed to attend the meetings but will have no voting status. Investigators and key trial personnel may be invited to join the SSC as appropriate to ensure representation from a range of centers and professional groups.

Notwithstanding the obligations of the Sponsor and the Coordinating Investigator assigned for this study, the SSC will be responsible for the overall governance of the trial and will meet by teleconference or in-person as required. The Sponsor will be responsible for administration of the study and for updating the SSC and Investigators and for the exchange of information between the Investigators and members of the SSC.

10.1.6 SAFETY OVERSIGHT

DSMB will be established to oversee the safety and efficacy of the trial. This board will be assembled according to GCP. List of members of the DSMB will be provided for inclusion in the trial master file and updates to the list will be provided during the trial.

Data analyses will be supplied, in confidence, to the DSMB, which will be asked to give advice on whether the accumulated data from the trial, together with the results from other relevant research, justifies the continuing recruitment of further subjects. The DSMB will operate in accordance with a trial-specific charter based upon the template created by the Damocles Group (121). Members of the DSMB will be the only individuals who see the confidential, accumulating data from the trial; however, the Sponsor may receive subsets of the report, as seen fit by the DSMB (eg, accrual, compliance, data completeness). The board will meet as frequently as considered necessary, but at least semiannually, either in person or by teleconference.

The DSMB may consider recommending stopping the trial early if:

- the recruitment rate or data quality are unacceptable;
- there are cases of excessive safety concern that compromise subject safety; or
- results of any interim analysis indicate futility.

The DSMB may also recommend continuation beyond the planned number of subjects in the trial if it is felt that further information might be of interest. If this is recommended, it will be submitted as an amendment, for approval of the applicable IRBs prior to implementation.

Following each meeting, the DSMB will report their findings and recommendations to the Sponsor, or the SSC, should the latter be established in the study (see § 10.1.5 for details). No results relating to the trial will be made available to participants until the Sponsor (or the SSC, if established) considers the data sufficiently mature to justify such a course of action.

DSMB may recommend to the Sponsor or the SSC to suspend recruitment in the event of serious or persistent non-compliance and/or very poor recruitment.

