9.2 SAMPLE SIZE DETERMINATION

A sample size is calculated to test the null hypothesis with 80% power at a 5% two-sided level of significance using a two sample-t-test for simplicity, even though the main statistical analysis may employ a statistically more powerful model-based approach. The estimates used for the mean and standard deviation of the changes from baseline to day 90 are taken from the literature as well as company pilot study data. In the pilot study, the mean change in mRS score from baseline to week 9 in the treatment group was -2.5 (SD=0.66) versus -1.3 (SD=0.46) in the sham group. In the literature a difference of 0.06 points on the mRS between treatment groups is considered clinically meaningful (114). As powering the trial to detect this difference would yield infeasibly large sample sizes, sample size projections were based on detecting a difference as low as 40% of the difference seen in the pilot trial = 0.5-point. To detect a 0.5-point difference between the groups with 80% power at a 5% level of significance using a standard deviation of 1 point and 1:1 allocation ratio, the calculated sample size (PROC POWER in SAS V9.4) is 128 participants in total, 64 participants in each arm. Allowing for a 15% dropout, 150 participants should be randomized.

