9.4 STATISTICAL ANALYSES

9.4.1 GENERAL APPROACH

Statistical analyses will be performed using SAS® v9.4 or higher (SAS Institute, Cary, NC, USA). Statistical analyses and reporting will be performed in compliance with FDA Guidance E6 and E9 and ISO 14155;2020.

Study data will be summarized with descriptive statistics and presented in tables and figures. Continuous variables will be summarized by a mean, standard deviation, minimum, median, and maximum and categorical variables by a count and percentage. For comparison of continuous variables, the two-sample t-test or the Wilcoxon rank sum test will be used as appropriate. For comparison of proportions (categorical variables), the chi-squared test or Fisher's exact test will be used as appropriate. A Cochran-Armitage trend test may be used when the response is ranked. For comparison of time to event data, the log-rank test will be used. If multiple measurements are taken in a single subject, statistics described below will be appropriately modified to accommodate the within subject correlation.

Detailed methodologies of the statistical analyses of the data collected in this study will be outlined in a trial-specific Statistical Analysis Plan (SAP). Any changes to planned analyses will be described and justified in the SAP. Analyses outlined in the SAP take precedent over those defined in the protocol to the extent there are any conflicts between the two documents.

Significance Levels and Type I Error

The overall significance level for this study is 5% using two-tailed tests, except for the group by site interaction that will be tested at a significance level of 15%.

The hierarchy (stepwise gatekeeper) approach will be adopted for the primary and secondary endpoints to control type I error due to multiple endpoint testing.

The primary endpoint will be analyzed first and only if the null hypothesis is rejected at a 5% level of significance or lower then we shall continue to test the secondary endpoints in a hierarchical manner. Nominal p-values will be reported, even if eventually due to the hierarchy the result is not considered statistically significant.

	The efficacy of a frequency-tuned electromagnetic field treatment in facilitating the recovery of subacute ischemic stroke patients – a pivotal study		
	No. BQ5	Ver. 4	Page 80 of 150

The hierarchical order of analysis of the secondary endpoint family will be:

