The study will either continue to the originally planned sample size if the result is “favorable”, stop for futility if the result is “unfavorable” or an increase will be made to the sample size if the result is “promising”. These decisions will be made based on the conditional power (CP), defined as the conditional probability that the result will exceed a critical value at the interim given the observed effect size $\hat{\delta}_1$ = difference between mean change from baseline mRS score for the BQ 2.0 versus sham groups at the interim look.

Notation:

- n1= sample size at interim analysis.
- n2= original sample size calculated based on assumed effect size.

nmax = the highest sample size the company is willing to use, nmax = 292 subjects (344 randomized including an allowance for a 15% dropout), and is based on a potential smaller effect size of ~0.33.

CPmin = is the calculated minimum CP based on the ratios nmax/n2, n1/n2 and the target study power (80%).

The following are the decision rules for the interim analysis which will be performed upon accrual of ~61% (n1/n2) of the originally planned sample size, ie, 78 evaluable subjects. These depend on the zone into which CP falls at the interim, the calculated CPmin, the maximum sample size designated for the study and the % of the originally planned sample size at which the interim analysis will be performed. Following this principle does not inflate the Type I error.

	The efficacy of a frequency-tuned electromagnetic field treatment in facilitating the recovery of subacute ischemic stroke patients – a pivotal study		
	No. BQ5	Ver. 4	Page 84 of 150

- If the result is “Unfavorable”, ie, $CP < CP_{min} = 32.7375\%$, ie, interim result is so disappointing that it is not worth increasing the sample size to retrieve conditional power, stop the trial for futility.
- If the result is “Promising”, ie, $32.7375\% \leq CP < 80\%$ for the primary endpoint, the sample size is increased to recover the targeted power of 80%. The sample size used will be either the new calculated sample size based on the conditional power (117) or the predetermined maximum sample size of 292 (344 randomized including an allowance for a 15% dropout) subjects, whichever lower.

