- If the result is “Favorable”, ie, $CP \geq 80\%$ for the primary endpoint, the interim results are sufficiently favorable and the trial continues to the original sample size planned of 128 (150 randomized including an allowance for a 15% dropout) without the need to adaptively increase the sample size.

Controlling the Alpha Level for the Primary Endpoint

The overall alpha level for this study is 5%. Planning an interim analysis that permits an increase in the sample size as described above does not inflate the type I error (116, 118, 119), which means that the testing of the primary endpoint will be at a 5% level of significance.

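### Section 10.1.6 lets an unblinded DSMB recommend enrolling past the planned number outside the section 9.4.6 rule, and the protocol's type I error argument does not cover that route

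*Protocol*

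**What the plan says.** Section 9.4.1 sets the error rate: "The overall significance level for this study is 5% using two-tailed tests". Section 9.4.6 plans one interim analysis, "upon accrual of ~61% (n1/n2) of the originally planned sample size, ie, 78 evaluable subjects". The sample size may rise only if conditional power lies between 32.7375% and 80%, and to at most 292 evaluable (344 randomized). Below that zone the trial stops for futility, and above it the trial continues to 128 evaluable. Of this rule the protocol says: "Following this principle does not inflate the Type I error". It limits the claim to an increase made as that section describes, keeps the conventional final test, and concludes: "which means that the testing of the primary endpoint will be at a 5% level of significance".

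Section 10.1.6 gives the DSMB oversight of efficacy as well as safety, access to the accumulating data, and meetings at least twice a year. It then adds: "The DSMB may also recommend continuation beyond the planned number of subjects in the trial if it is felt that further information" seems of interest. Such a recommendation would go through an amendment approved by the IRBs. The same section words the futility stop as something the board may consider advising, whereas 9.4.6 states it as the action to take.

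**The concern.** The conventional test keeps its level under 9.4.6 because the increase happens once, at a fixed look, only for interim results in a defined zone, and up to a fixed cap. The sentence in 10.1.6 opens a second route with none of these limits, to a board that knows the comparative results. If that route were used because a result fell short, the trial would get a further chance at the unadjusted critical value. A positive pivotal result could then be challenged as not being a 5% test, and the argument in 9.4.6 would be no answer, since it does not reach this case.

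**Working it through.** Success requires a difference in favour of the device, so the relevant nominal level is 2.5% one-sided (critical value 1.96).

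**1. The plan's own figures.** Section 9.2 gives a difference of 0.5, SD 1 and 80% power. The two-sample t-test has 80.1% power at 64 per arm and 79.5% at 63, which confirms that the size "is 128 participants in total, 64 participants in each arm". The interim fraction is 78/128 = 0.609.

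The lower zone limit also reproduces. With n1 = 78, n2 = 128 and N = 292, the interim z1 at which the conventional test is just safe solves

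[√((N − n1)/(n2 − n1)) × (1.96√n2 − z1√n1) + z1√n1] / √N = 1.96,

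which gives z1 = 1.312. Conditional power under the observed trend is then

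Φ(z1√(50/78) − (1.96√128 − z1√78)/√50) = Φ(1.050 − 1.497) = Φ(−0.447) ≈ 32.74%,

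against 32.7375% stated. Conditional power of 80% corresponds to z1 ≈ 1.94.

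**2. Where null trials go at the interim.** Φ(1.312) = 90.5% fall in the unfavourable zone, 6.9% in the promising zone and 2.6% in the favourable zone.

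**3. Planned rule alone.** Given z1 and final size N, the null probability of rejection is 1 − Φ((1.96√N − z1√78)/√(N − 78)). Integrating over z1, with N set by the 9.4.6 rule:
- futility stop obeyed: about 1.84%
- futility stop not obeyed (unfavourable trials run on to 128): about 2.40%

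Both are below 2.5%, so the claim in 9.4.6 holds for the rule it describes.

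**4. Adding the 10.1.6 route.** The protocol gives no extension rule, so these scenarios are assumptions. A non-significant final result is extended by 32 to 200 subjects and retested at 1.96 (simulation under the null).

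| Scenario | Futility obeyed | Futility non-binding |
|---|---|---|
| Planned rule only | 1.84% | 2.40% |
| Extend near misses (final z between 1.0 and 1.96) | 2.2% to 2.3% | 3.3% to 3.5% |
| Extend any non-significant final result | 2.2% to 2.3% | 3.3% to 4.2% |
| Continue unfavourable trials to 292 instead of stopping | not applicable | 3.2% |

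The last row needs no second final look. It arises if the board, having seen an unfavourable interim result, recommends more subjects instead of stopping.

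**The case against.** The strongest objection concerns size. A reader might start from 128 evaluable subjects, extend when z falls short of 1.96, and infer that the error rate is simply 3.5% to 4.2%. The documents do not support that as an unconditional figure. It treats every null trial as reaching 128, whereas the rule in 9.4.6 stops about 90.5% of them at 78. With that stop obeyed, even extending every non-significant final result stays below 2.5%. This part of the objection stands. It does not settle the matter, because the protocol does not secure the safe path: 10.1.6 leaves the futility stop to the board's consideration and does not exclude unfavourable trials from extension.

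A reader might also infer that the board can extend at any time, for any reason, with an unadjusted test. That is too strong. The board only recommends, an IRB-approved amendment must come first, and that amendment could specify a suitable test. The 5% statement in 9.4.6 is tied to its own rule, so an unadjusted test after a 10.1.6 extension is an inference. Still, nothing in the clause requires an adjustment, and approving more patients changes neither the critical value nor the test statistic.

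The sentence might be read as merely pointing to the 9.4.6 increase. The amendment requirement speaks against this, since that increase is already in the protocol, and the trigger is different.

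Finally, the DSMB charter and the SAP are not at hand and may narrow the discretion. The point here is a permission that the protocol itself grants, not a detail left to those documents.

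**Conclusion.** The point holds in a conditional form. Section 10.1.6 permits an extension informed by comparative data that lies outside the reasoning by which 9.4.6 keeps a conventional 5% test. Inflation is not automatic. With futility strictly obeyed, the one-sided error is about 1.84% under the planned rule and about 2.2% to 2.3% with an end-of-trial extension. With futility treated as non-binding, it is about 3.3% to 4.2% when non-significant final results are extended by 32 to 200 subjects, and about 3.2% when unfavourable trials continue to 292.

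These figures assume approximately normal test statistics, conditional power under the observed trend (which reproduces the stated 32.7375%), a retest at 1.96, and extension patterns chosen for illustration. The protocol's claim should not rest on slack from a futility stop that its own text leaves discretionary. The matter merits correction because the repair costs almost nothing, not because a breach is certain.

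**What to change.** Delete the sentence in 10.1.6, or replace it with text to this effect: the sample size may be increased only once, at the planned interim analysis, in the promising zone of section 9.4.6, and to no more than 292 evaluable (344 randomized) subjects; any other increase must be decided without access to arm-level data, or the final analysis must use a method that preserves the conditional error of the original design. Carry the same wording into the DSMB charter.

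With this change the planned rule stays below 2.5% one-sided whether or not futility is obeyed (about 1.84% or 2.40%), so the error claim no longer depends on how the futility wording is read. The cost is one sentence in each document and the loss of an unadjusted discretion for the board. Its power to recommend stopping is untouched.
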